#### **4.6.2.2 Carbohydrate metabolism**

Fasting plasma glucose, insulin levels and glycosylated hemoglobin (HbA1C) are measured at baseline (start of treatment), at 6 and 12 months, then annually during GH treatment, and at the end of treatment. An OGTT is performed at the same time points.

The OGTT is a provocation test to examine the efficiency of the body to metabolize glucose. The OGTT provides information on latent diabetes states.

Insulin resistance will be estimated using both the homeostasis model assessment (HOMA) and quantitative insulin sensitivity check index (QUICKI)

$$\text{HOMA} = \frac{\text{fasting insulin } (\mu\text{U/ml}) \times \text{fasting glucose } (\text{mg/dl})}{405^*}$$

\*use constant 22.5 instead of 405 if glucose concentration is reported in mmol/L

$$\text{QUICKI} = \frac{1}{\log \text{fasting insulin } (\mu\text{U/ml}) + \log \text{fasting glucose } (\text{mg/dl})}$$

Carbohydrate metabolism data will be listed per parameter and will include: visit, sample date, parameter result, reference range, outside reference range indicator, clinical significance and a column containing comments.

Carbohydrate metabolism data as well as HOMA and QUICKI scores will be summarized by parameters and visit for the SAF for absolute values, and absolute and relative changes from baseline.

Shift tables for changes in the reference range classification as compared to baseline will be prepared for fasting plasma glucose, fasting insulin levels and HbA1C. The categories "low", "normal", "high" and "Missing" will be used in the shift tables. Shifts between categories will be displayed using absolute counts. Percentages will be provided per baseline category (without considering missings) for each post-baseline category, and based on all non-missing patients for total line/column.

In addition number and percentage of patients with DM and without DM finding will be presented. Patients fulfilling any criteria for DM given in section 4.5 will be regarded as patients with DM, patients not fulfilling any criteria on at least one visit will be considered as patients without DM finding.

Implausible insulin or glucose values will be excluded, i.e. Glucose values below 0.1 mmol/L and insulin values below 0.1 pmol/L will not be used for the calculation of HOMA and QUICKI.

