In the same study ([Hokkon-Koelega et al 2004](#), [Sas et al 2001](#)), all 79 children underwent standard oral glucose tolerance tests at baseline, after 1 and 6 years of GH treatment and 6 months after discontinuation of GH therapy. Before GH therapy 8% of the children had impaired glucose tolerance (IGT) according to WHO criteria. IGT was found in 4% of children after 6 years of therapy and in 10% of children after stopping GH treatment. GH therapy induced considerably higher fasting and glucose-stimulated insulin levels, indicating insulin resistance. After discontinuation of GH therapy the mean serum glucose levels remained normal and the mean serum insulin levels decreased significantly, to normal age-matched reference values. HbA1C levels were always in the normal range and none of the children developed diabetes mellitus.

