### 2.1 Study documents and general considerations

This document describes the procedures and conventions to be used for the final analysis of all patients who were included into study EP00-401 and is based on study protocol V6.0, dated 07-Feb-2020, incorporating amendment no. 05.

Raw data listings, summary tables, graphs and statistical tests will be generated by means of the program SAS 9.4 and SAS/STAT Version 14.3.

The following descriptive statistical parameters will be shown in summary tables

- Continuous variables: n (valid cases), n (missing data), mean, standard deviation (SD), min, 1st quartile (Q1), median, 3rd quartile (Q3), max
- Categorical variables: Count and percentage of category. Percentages are routinely based on the total category count excluding the missing category if not otherwise mentioned. Percentages showing a rate relative to the total number of patients in this group are given in special tables (e.g. Adverse Event (AE) tables). Footnotes will specify the percent basis.

For continuous variables, if not otherwise specified, mean, median and standard deviation values will be reported to one decimal place greater than the data were collected. Minimum and maximum values will be reported with the same precision, as they were collected.

Generally, percentages will be displayed in the format xx.d, i.e. one decimal place will be shown; if the calculated percentage is 100, no decimal is required (i.e. 100% and not 100.0%). If the count is zero no percentage needs to be shown.

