## 2.3 Endpoints

### 2.3.1 Primary endpoint

The development of diabetes is the primary endpoint of the study and is evaluated on the basis of the carbohydrate metabolism (fasting plasma glucose (FPG), oral glucose tolerance test (OGTT)) and HbA1C.

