## 2.5 Determination of sample size

There was no formal sample size calculation for this study which is intended to exploratorily investigate the long-term effect of the treatment with respect to the development of diabetes. No such incidences are currently available to allow for a rigorous sample size estimation. Results obtained in this study will be compared to data published in the literature.

[REDACTED]  
Patients dropping out before completing 1 year of treatment will be replaced.

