#### **Impaired Fasting Glucose (IFG):**

FPG 110 - 125 mg/dl (6.1 - 6.9 mmol/l)

and

2-h plasma glucose  $<$  140 mg/dl ( $<$ 7.8 mmol/l)

The identification of diabetes mellitus on laboratory results had to be in accordance to the documentation of diabetes mellitus as an AE.

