##### **4.6.2.1 Adverse events**

Adverse events (AEs) are to be recorded during the whole study period.

AEs are coded according to Novartis MedDRA, Version 24.1.

The AE data will be listed, sorted by site code, patient number, and preferred term. This list will include: adverse event, MedDRA system organ class, MedDRA preferred term, start date, stop date, intensity, outcome, relationship to study drug, action taken, and a variable indicating whether an AE was considered a serious adverse event (SAE).

AEs starting prior to start of treatment will not be included in the summary tables, but listed only.

A general summary table of AEs will contain the total number of AEs, the total number of SAEs, and separate descriptions of the splits for the variables relationship to study drug, action taken,

outcome and intensity. Outcome is categorized according to the CRF as “resolved” (i.e. resolved completely or resolved with sequelae), “ongoing”, “fatal” or “unknown”.

The incidence of an AE is defined as the number of patients who experience that event, divided by the number of patients in the SAF population. With AE incidence, each event will be counted only once for a given patient. More specifically, if a patient reports the same event more than once, as determined by preferred term and system organ class, that patient will be counted only once for the incidence of the AE. For example, when a patient reported three instances of headache, this patient counts only once towards the total incidence of headache. Incidence of events within a system organ class is defined similarly. Whenever incidence is cross-tabulated with intensity in the summary tables, the incidence of an AE will be calculated for each level of intensity, i.e., the number of patients who experience that AE on a certain level of intensity.

Incidence tables will provide information about rates of AEs per patient-year, calculated as  $\{(number\ of\ patients\ who\ experience\ that\ event)\ / (years\ of\ exposure)\}$ . Additional tables will enable a direct comparison of formulation specific rates of events per patient year.

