**TABLE 14.3-3.7 SUMMARY OF PATIENTS WITH LABORATORY PARAMETERS FULLFILING THE DEFINITION OF DIABETES MELLITUS (DM) (SAF)**

	Total	Number of patients with DM (%)	Number of patients without DM finding (%)
Female	XXX	XX (XX.X%)	XX (XX.X%)
Male	XXX	XX (XX.X%)	XX (XX.X%)
Total	XXX	XX (XX.X%)	XX (XX.X%)

DM is defined as fulfilment of one of the following criteria:

1. FPG  $\geq 126$  mg/dl ( $\geq 7.0$  mmol/l) during safety lab assessment or as -10min value of OGTT
2. 2-h plasma glucose  $\geq 200$  mg/dl ( $\geq 11.1$  mmol/l) during OGTT
3. HbA1C  $\geq 6.5\%$

Patients not fulfilling at least one criteria on at least one visit are considered as patients without DM finding

**TABLE 14.3-3.7.1 SUMMARY OF OVERWEIGHT\* PATIENTS AT BASELINE WITH LABORATORY PARAMETERS FULLFILING THE DEFINITION OF DIABETES MELLITUS (DM) (SAF)**

Sex	Total	Number of patients with DM (%)	Number of patients without DM finding (%)
Female	XXX	XX (XX.X%)	XX (XX.X%)
Male	XXX	XX (XX.X%)	XX (XX.X%)
Total	XXX	XX (XX.X%)	XX (XX.X%)

\* Defined by international cut off points for BMI for overweight by sex and age at baseline. The cut-off point is defined by the percentile that passes through BMI at 25 kg/m^2 at age 18.

DM is defined as fulfilment of one of the following criteria:

1. FPG  $\geq 126$  mg/dl ( $\geq 7.0$  mmol/l) during OGTT or safety lab assessment
2. 2-h plasma glucose  $\geq 200$  mg/dl ( $\geq 11.1$  mmol/l) during OGTT
3. HbA1C  $\geq 6.5\%$

Patients not fulfilling at least one criteria on at least one visit are considered as patients without DM finding

**TABLE 14.3-3.8 SUMMARY OF PATIENTS WITH LABORATORY PARAMETERS FULLFILING THE DEFINITION OF IMPAIRED GLUCOSE TOLERANCE (IGT) (SAF)**

	Total	Number of patients with IGT (%)	Number of patients without IGT finding (%)
Female	XXX	XX (XX.X%)	XX (XX.X%)
Male	XXX	XX (XX.X%)	XX (XX.X%)
Total	XXX	XX (XX.X%)	XX (XX.X%)

IGT is defined as fulfilment of all of the following criteria:

1. FPG < 126 mg/dl (<7.0 mmol/l) during OGTT or safety lab assessment
2. 2-h plasma glucose between 140 – 200 mg/dl (≥7.8 and <11.1 mmol/l) during OGTT

Patients not fulfilling all criteria on at least one visit are considered as patients without IGT finding

**TABLE 14.3-3.9 SUMMARY OF PATIENTS WITH LABORATORY PARAMETERS FULLFILING THE DEFINITION OF IMPAIRED FASTING GLUCOSE (IFG) (SAF)**

	Total	Number of patients with IFG (%)	Number of patients without IFG finding (%)
Female	XXX	XX (XX.X%)	XX (XX.X%)

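### Laboratory-defined diabetes, the binary primary endpoint, is to be reported only as a count and percentage, with no confidence interval and no person-time rate

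*SAP*

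**What the plan says.** SAP 2.3.1 states: "The development of diabetes is the primary endpoint of the study". SAP 4.5, the section on analysing that endpoint, defines diabetes, impaired glucose tolerance (IGT) and impaired fasting glucose (IFG) from laboratory values, but names no estimator. It adds one sentence linking the laboratory and adverse-event records: "The identification of diabetes mellitus on laboratory results had to be in accordance to the documentation of diabetes mellitus as an AE".

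The summary itself is in SAP 4.6.2.2: "In addition number and percentage of patients with DM and without DM finding will be presented". The Table 14.3-3.7 shell has rows for females, males and all patients. Its columns are the total, those with DM, and those without a DM finding. Its footnote reads: "Patients not fulfilling at least one criteria on at least one visit are considered as patients without DM finding". SAP 2.1 adds a general display rule: "If the count is zero no percentage needs to be shown".

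On use of the result, SAP 2.5 says: "Results obtained in this study will be compared to data published in the literature". Protocol 1.2.4 describes one such source, 79 GH-treated children born SGA, and reports that "none of the children developed diabetes mellitus".

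Intervals and rates do appear elsewhere in the SAP. Sections 2.4 and 4.6.1 plan 95% intervals for mean changes in the efficacy endpoints. Section 4.6.2.1 plans person-time rates for adverse events: "Incidence tables will provide information about rates of AEs per patient-year, calculated as" patients with the event over years of exposure.

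**The concern.** This is a safety study of diabetes risk, and its main answer may rest on zero or a handful of cases. A count and percentage do not show how much risk such a result rules out, which is what a reader needs from it.

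An ever-positive percentage also has no stated time horizon, and follow-up here is very uneven. Protocol 6.5.9 foresees withdrawal before one year. The Study status section of the protocol shows 32 patients still on treatment more than nine years after the last enrolment. A percentage pooled over such follow-up is hard to set beside a published figure from another schedule. Lesser endpoints in the same SAP get intervals or patient-year rates; the primary endpoint gets neither.

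**Working it through.** **Inputs.** Enrolled: 278 (Protocol, Study status). Excluded from the safety set: 1 (note to SAP Table 14.1-2). Printed safety-set size: N=277 (SAP Table 14.3-1.1). Last enrolment 29-Apr-2010, with 32 patients still treated on 31-Dec-2019 (Protocol, Study status). Screening lasts up to 8 weeks (Protocol 7). The cited study had 79 children (Protocol 1.2.4). Event counts and mean exposure are not given, so the values used below are assumptions.

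**1. Denominator.** 278 − 1 = 277, which reproduces the printed N.

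**2. Precision of the percentage.** Exact (Clopper-Pearson) two-sided 95% limits. With zero cases the upper limit is 1 − 0.025^(1/n).

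- 0/277: 1 − 0.025^(1/277) = 1.32%
- 1/277 = 0.36%: 0.01% to 1.99%
- 3/277 = 1.08%: 0.22% to 3.13%
- 0/79 (cited study): 1 − 0.025^(1/79) = 4.56%

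**3. Spread of follow-up.** From 29-Apr-2010 to 31-Dec-2019 is 9.67 years. Less 56 days of screening, this is 9.52 years. Each of the 32 patients therefore spans at least about 9.5 years from the start of treatment. At the other end, some patients may have under 1 year.

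**4. Rate.** Patient-years = 277 × mean exposure. Exact Poisson 95% limits on the count are 0 to 3.689 for zero events and 0.619 to 8.767 for three. Dividing by patient-years gives, per 1000 patient-years:

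| Assumed mean exposure | Patient-years | 0 cases: upper limit | 3 cases: rate (95% CI) |
|---|---|---|---|
| 4 years | 1108 | 3.3 | 2.7 (0.56 to 7.9) |
| 6 years | 1662 | 2.2 | 1.8 (0.37 to 5.3) |
| 8 years | 2216 | 1.7 | 1.4 (0.28 to 4.0) |

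The same zero thus carries a limit that varies about twofold with exposure, and the planned table does not show exposure.

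**5. Total exposure as a stand-in for time at risk.** It adds two kinds of excess time.

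- Time after a first positive: three cases each treated 10 more years add 30/1108 = 2.7%.
- Time after the last glycaemic test in patients who leave: as an illustration, 20% of 277 is about 55 patients, and one extra year each adds 55/1108 = 5.0%.

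Both push the rate down.

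**6. Untested patients.** The safety set requires any post-baseline safety assessment (SAP 2.6), and Visit 02 has no glucose test (Protocol 7.1.3). If 20 patients had no post-baseline glycaemic test, the zero-case upper limit becomes 1 − 0.025^(1/257) = 1.43%, against 1.32%.

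**7. Baseline positives.** Neither SAP 4.6.2.2 nor the Table 14.3-3.7 footnote limits a positive to post-baseline visits. The protocol excludes known diabetes and raised fasting glucose or OGTT values at entry, but sets no HbA1c limit. Few baseline positives are to be expected, but no rule covers them.

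**The case against.** The strongest reply is that the study is exploratory, has no hypothesis or formal sample size, and promises no interval for any proportion. That is true, and it is why this is not an error in a stated figure. It does not argue against an exact interval, which is descriptive and tests nothing.

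Four stronger readings are tempting, and the documents do not support them.

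- *That the endpoint has no other analysis.* SAP 4.6.2.2 plans by-visit glycaemic summaries with changes from baseline, HOMA and QUICKI scores, and shift tables. Tables 14.3-3.8 and 14.3-3.9 cover IGT and IFG, and SAP 5.5 lists diabetes and hyperglycaemia adverse events. None of these states the precision or time scale of the binary endpoint.
- *That a zero would be uninterpretable.* The shell prints the total beside it, so a reader could compute the interval. The display rule in SAP 2.1 permits dropping the percentage but does not require it. A primary result should still not depend on the reader's own calculation.
- *That person-time is ignored.* AE-coded diabetes gets a crude rate, laboratory cases are meant to agree with AE records, and exposure is summarised in Table 14.1-4. But the AE rate is by preferred term, has no interval, and is not the laboratory endpoint.
- *That untested patients distort the result.* The effect in step 6 is small. A final visit with glucose and OGTT is planned for patients who stop. The wording in SAP 4.6.2.2 can also be read as requiring an assessed visit.

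Two cautions stand. The contrast between 0/277 and 0/79 concerns sampling precision only, because the cited study tested at baseline, 1 and 6 years, and 6 months after stopping. And an interval or rate does not by itself make the literature comparison valid. A single rate averages over childhood and puberty, and any one positive criterion counts, with fasting-glucose retests only listed (SAP 4.1).

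**Conclusion.** The point holds as a reporting gap that should be closed: the planned summary of laboratory-defined diabetes gives neither precision nor a time scale. On N=277, zero cases leaves a risk of up to 1.32% open, and three cases would span 0.22% to 3.13%. The rate limits of 3.3, 2.2 and 1.7 per 1000 patient-years rest on assumed mean exposures of 4, 6 and 8 years; the report will supply the real figure. The data needed are already collected and listed, so nothing is lost. The count of untested patients is a minor clarification and does not carry the point.

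**What to change.** In SAP 4.6.2.2 and Table 14.3-3.7:

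1. Add an exact Clopper-Pearson 95% interval for the percentage with DM. Show it also when the count is zero, as a stated exception to SAP 2.1.
2. Count as incident cases only patients whose first positive criterion is post-baseline, and list baseline positives separately.
3. Add patient-years from first dose to first positive or last glycaemic assessment, and the rate per 1000 patient-years with an exact Poisson 95% interval. Footnote that onset is known only to the assessment interval (6-monthly in year 1, then annual) and that a single rate is an average over follow-up.
4. If total exposure is used as a fallback, say that it includes treatment time after the last test, so the rate is somewhat understated (about 5% in the illustration above).
5. As a minor clarification, show the number with at least one post-baseline glycaemic test beside the safety-set total.

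Extending this to Tables 14.3-3.7.1, 14.3-3.8 and 14.3-3.9 is optional. The cost is a few table columns and a little programming. Study conduct and the laboratory thresholds for DM stay as they are; item 2 only adds a timing rule for incident cases.

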### **6.5.9 Study drug discontinuation**

Treatment can be terminated at any time, at the discretion of the investigator or the Sponsor, or at the patient's request, in the event of an AE or due to treatment failure.

Study drug treatment has to be discontinued in the following cases during treatment period:

- Occurrence of overt diabetes mellitus; defined as fasting blood glucose  $\geq 126$  mg/dl or  $\geq 7.0$  mmol/l and abnormal findings in OGTT defined by  $\geq 200$  mg/dl or  $\geq 11.1$  mmol/l after 120 minutes. For further instruction see appendix
- Requirement of an increase of the recommended dose to obtain increased growth velocity
- Renal transplantation
- Diagnosis of benign intracranial hypertension
- Malignancy
- Pregnancy
- Withdrawal of informed consent
- Treatment failure

Treatment failure is defined as: Inadequate response to treatment, e.g. height velocity standard deviation score (HVSDS) below +1 in the first year.

Furthermore a standardized controlled procedure for the calculation of the treatment response (via "Treatment Response Control Fax") was implemented (see also 6.5.3 treatment duration) to ensure a unified flawless computation and to authorize treatment continuation, if applicable (managed by Data Management at Metronomia). In case the Investigator does not agree with the assessment by Data Management, Sandoz is informed and initiates the re-assessment of the treatment response data via an independent specialist reader.

Patients who are withdrawn from the study before completing at least one year of treatment with Omnitrope® will be replaced.

Study drug must be discontinued if the investigator concludes that continuation would result in significant safety risk for that patient and in the event of pregnancy.

Patients who discontinue study drug before completing the study should not be considered withdrawn from the study and should be scheduled for a final visit as soon as possible, at which time all of the assessments for the final visit will be performed.

A Study Drug Discontinuation form should be completed, giving the date and reason for stopping the study drug. All patients who discontinue study drug, including those who refuse to return for a final visit, will be contacted for safety evaluations during the 4 weeks following the last dose of the study drug.

Patients who discontinued this study for any reason will not be able to re-enter the study.

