## 7 Visit Schedule and assessments

The Flow Chart (synopsis) lists assessments and indicates with an “X” the visits during which they are performed. Patients should be seen for all visits at the designated time-point or as close to it as possible. A time window for the visits of up to +/- three weeks will be allowed.

All data obtained from the assessments listed in the Flow-Chart and described in detail in the subsections below must be supported in the patient’s source documentation.

The study visit schedule consists of screening period for up to 8 weeks prior to the initiation of therapy followed by an open treatment period until final height is reached. The study plan timetable (please refer to the Flow Chart Treatment Period) indicates the number and timing of the planned visits. During these visits, the mentioned efficacy and safety parameters will be assessed. It is important to maintain the visit schedule during the treatment period as accurately as possible. If any individual visit date does not conform to the planned schedule, the subsequent visit should be realigned to maintain the schedule relative to the start of the treatment period.

The clinical and laboratory investigational plan per visit is summarized in the Flow Chart Treatment Period.

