### Handling of elevated blood glucose levels and OGTT

Fasting blood glucose levels	OGTT	Patient outcome
impaired	impaired	Ongoing
overt	impaired	Ongoing
overt	overt	Discontinuation

As the OGTT is more sensitive than fasting blood glucose assessment, the final decision with regards to discontinuation will be eventually based on the result of the OGTT.

In case of the unlikely situation that fasting blood glucose levels = normal/impaired and OGTT=overt, patient outcome = discontinuation.

Overt levels are defined as:

- Fasting blood glucose  $\geq 126$  mg/dl or  $\geq 7.0$  mmol/l
- OGTT  $\geq 200$  mg/dl or  $\geq 11.1$  mmol/l after 120 minutes

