#### Alignment of final visits

A final visit should be performed for all patients terminating study drug. These visits will be analyzed together with the regularly performed study visits. A final visit will be assigned to the appropriate study visit as follows:

In a first step the respective limit between two visit used for assignment, will be assessed as follows: limit = (Day on which VX [= Visit X] should have been performed - Day on which VX-1 should have been performed)/2. The respective limit was rounded if necessary. Days on which a visit should have been performed according to protocol will be assessed as follows (excluding V0 and V1): Month given in the protocol \*(365.25/12) (i.e. V2 = Day 92, V3 = Day 183, V4 = 274 ...).

In a second step final visits performed between VX-1 and the limit (included) will be assigned to VX-1, final visits performed after the limit and prior to VX will be assigned to VX.

For example: A final visit performed between V3 and V4, will be assigned to V3, if performed at or before Day 229 (= (Day 274 + Day 183)/2 = 228.5 => rounded to 229). If performed after Day 229 and at or before V4, the final visit will be assigned to V4.

If due to the assignment of final visits to regular visits two assessments are available for one visit, the assessment nearest to the day on which the visit had to be performed will be used.

If the final visit was performed on the same day as a regular visit, the regular visit will be used for analysis.

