#### Retest of fasting blood glucose

Retest values for fasting blood glucose will be listed only.

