**TABLE 14.3-3.11 SUMMARY OF ANTI-HCP ANTIBODIES (SAF)**

Visit	Total	Missing	N	Number of patients with positive test result (%)
V01	XXX	XXX	XXX	XX (XX.X%)
V02	XXX	XXX	XXX	XX (XX.X%)
V03	XXX	XXX	XXX	XX (XX.X%)
V04	XXX	XXX	XXX	XX (XX.X%)
V05	XXX	XXX	XXX	XX (XX.X%)
V07	XXX	XXX	XXX	XX (XX.X%)
V...	XXX	XXX	XXX	XX (XX.X%)
Total*	XXX	XXX	XXX	XX (XX.X%)

\* including all final assessments

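### As written, the diabetes count is not limited to post-baseline values, and the nearest-day rule, read literally, could remove a child's only qualifying value

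*SAP*

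**What the plan says.** Protocol 3.1 and SAP 2.2 set the primary objective as the development of diabetes during treatment. SAP 4.5 defines diabetes by any one of three laboratory criteria: fasting glucose, 2-hour OGTT glucose or HbA1c. SAP 4.6.2.2 lists baseline among the measurement times and then states: "Patients fulfilling any criteria for DM given in section 4.5 will be regarded as patients with DM". The footnote to Table 14.3-3.7 adds: "Patients not fulfilling at least one criteria on at least one visit are considered as patients without DM finding".

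SAP 4.1 maps each final visit to a scheduled visit number. Where this leaves two assessments for one visit, "the assessment nearest to the day on which the visit had to be performed will be used". The rule stands under general considerations and names no exception.

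Three protocol rules bear on how often two visits meet:
- Section 7, on timing: "A time window for the visits of up to +/- three weeks will be allowed".
- The appendix on elevated glucose, for a child whose fasting value is not overt: "OGTT=overt, patient outcome = discontinuation". The outcome is the same when both tests are overt.
- Section 6.5.9, for children who stop study drug: they "should be scheduled for a final visit as soon as possible", with all final-visit assessments.

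One other table does address final visits. The total row of Table 14.3-3.11 (anti-HCP antibodies) is marked "including all final assessments". The diabetes, IGT and IFG tables carry no such note.

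**The concern.** The count could err in either direction. A finding present before the first dose could be counted as diabetes that developed on treatment. A finding made on treatment could be left out because another assessment under the same visit number lay nearer the planned day.

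Either matters because few cases are expected. The GH-treated cohort described in Protocol 1.2.4 had none among 79 children (exact 95% upper limit 4.6%), and SAP 2.5 says the results will be compared with published data. With a handful of cases, one child can decide whether the report says none or some.

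**Working it through.** **1. Baseline values.** Exclusion criteria 3 to 5 (Protocol 5.1.2) bar known diabetes, fasting glucose of 5.6 mmol/l or more, and 2-hour glucose of 7.8 mmol/l or more. A baseline glucose case would therefore be an enrolment deviation. No criterion concerns HbA1c. The flow chart places HbA1c at Visit 01, where the first injection is also given (Protocol 7.1.2). A Visit 01 HbA1c of 6.5% or more meets SAP 4.5 and enters the count. By contrast, SAP 4.6.2.1 keeps adverse events that start before treatment out of the summary tables.

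**2. The plan's own alignment figure.** Planned day = month × 365.25/12. Month 6 gives 182.6, Day 183; month 9 gives 273.9, Day 274. The limit is (183 + 274)/2 = 228.5, rounded to 229, which matches SAP 4.1. Month 36 gives 1095.75, Day 1096. Month 42 gives 1278.4, Day 1278 by ordinary rounding, so the limit after month 36 is (1096 + 1278)/2 = Day 1187.

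**3. Annual value displaced.** Suppose the annual visit is *d* days early and the final visit follows *g* days later. The final visit is nearer the planned day if |g − d| < d, that is, if g is between 1 and 2d − 1.
- d = 7: g from 1 to 13 days; d = 14: 1 to 27; d = 21: 1 to 41.
- Example: overt OGTT on Day 1080 (16 days early), final visit on Day 1101 (5 days late). The final visit is used and the OGTT that stopped treatment is not.

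Assume annual visits are spread evenly over the 43 days from −21 to +21:

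| Final visit after | Annual value displaced | Annual value kept | Exact tie |
|---|---|---|---|
| 7 days | 18/43 = 42% | 25/43 | 0 |
| 14 days | 14/43 = 33% | 28/43 | 1/43 |
| 21 days | 11/43 = 26% | 32/43 | 0 |
| 28 days | 7/43 = 16% | 35/43 | 1/43 |

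If the final visit instead falls evenly over the year after the annual visit, simulation for month 48 gives about 3% of annual values displaced.

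**4. Final-visit value dropped.** An annual visit inside its window is at most 21 days from Day 1096. A final visit on Days 1118 to 1187 (70 days) is farther away, maps to month 36 and always loses. Under the same even-over-the-year assumption, about 23% of final values are dropped.

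**5. What one child is worth.** Table 14.3-1.1 gives a safety set of 277, and 1/277 = 0.36%. Exact (Clopper-Pearson) 95% intervals are 0/277: 0 to 1.32%; 1/277: 0.01 to 1.99%; 2/277: 0.09 to 2.58%.

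**The case against.** The strongest reply is that these cases have a second route into the report. SAP 4.5 says laboratory diabetes had to accord with its documentation as an adverse event. An overt OGTT that ends treatment could hardly be judged clinically irrelevant, so Protocol 7.4.7 makes it an adverse event. It would appear in the incidence tables, which leave out pre-treatment onset, and in listing 16.2.5.3. This stands as a partial safeguard. However, SAP 4.5 gives no rule for discordant cases, and the counting rule in 4.6.2.2 does not refer to adverse events.

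Second, the nearest-day rule may be meant only for by-visit summaries. Table 14.3-3.7 has no visit column, and it pools fasting values from the safety laboratory and the OGTT. That is a reasonable reading and may be the intended one, but the SAP does not state it. The anti-HCP footnote cuts both ways: it shows all final assessments entering a patient-level total, and it shows that the SAP says so when it means so.

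Third, a high Visit 01 HbA1c would be visible as the maximum in Table 14.3-2.4, and nothing in the documents suggests that such a child exists. This is true, but seeing the value does not take it out of the count.

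Three stronger readings are tempting, and the documents do not support them.
- A reader might take the 16% to 42% as lost cases. They are displacement fractions under an assumed spread of visits. A case is lost only if no fasting, OGTT or HbA1c value at the repeated final assessment or at any other visit qualifies.
- A reader might infer from "Retest values for fasting blood glucose will be listed only" that the headline count is wrong for lack of confirmation. Counting any single value is the plan's disclosed definition; a confirmed count would be an addition, not a correction.
- A reader might infer that a fasting glucose of exactly 126 mg/dl is lost on conversion, because SAP 4.6.2.5 names rounding only for IGT and IFG. SAP 4.5 states the limit in mg/dl, so that value can qualify directly.

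**Conclusion.** Two points hold on the text. The diabetes count has no post-baseline limit, so a Visit 01 HbA1c of 6.5% or more would count as diabetes developed on treatment. Read literally, the nearest-day rule also applies to this count and could remove a child's only qualifying annual or final-visit value.

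The second point rests on that literal reading, on two visits sharing a visit number and on no other value qualifying. The documents give no basis for the probability of all three together, so the number of lost cases is unknown and probably small. Each child moved in either direction changes the result by 0.36 percentage points. The study is descriptive and has no threshold to cross, but this is its primary, rare-event count, and its rule should not be left to interpretation at programming. The change is worth making. The WHO 2016 definition itself is not in question.

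**What to change.** In SAP 4.6.2.2 and Tables 14.3-3.7, 14.3-3.7.1, 14.3-3.8 and 14.3-3.9:
- Count only values obtained after the first dose, treat Visit 01 samples as baseline, and show baseline findings in a separate row.
- State, with a cross-reference in SAP 4.1, that the nearest-day selection applies to by-visit summaries only. The any-visit tables then use every post-baseline scheduled and final-visit value, with a footnote like that of Table 14.3-3.11.

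The cost is one extra row and a footnote, on data already collected.

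Optional clarifications, which do not correct errors in the primary count: a confirmed-count row that uses retests, beside the any-value headline and not in its place; wording on the unit in which the limits are applied; and a cross-tabulation of laboratory diabetes against diabetes adverse events.
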